### **3.5. Prior and Concomitant Medications**

Concomitant medications of interest is collected on the eCRF at baseline and at each on-drug visit. The number of subjects receiving medication in pre-specified categories, such as insulin, sulphonylurea, metformin, statin, anti-thrombotic, diuretic (loop, and non-loop), renin angiotensin aldosterone system (RAAS) inhibitor, will be presented by treatment group at baseline and during on-drug period. In addition, SGLT2 inhibitor use during the off-drug follow-up period will be summarized by treatment group.

## **4. EFFICACY**

The analysis will be performed based on the ITT analysis set, if not otherwise specified.

All statistical tests, except those for the primary and secondary efficacy endpoints, will be considered nominal and reported with a 2-sided 95% confidence level.

Unless otherwise stated, all efficacy analyses and summaries will be performed using the treatment groups assigned by IWRS.

### **4.1. Primary Efficacy Endpoint**

Subjects without baseline and/or post-baseline ACR measurements will be excluded from the primary efficacy analysis. Furthermore, subjects with macroalbuminuria at baseline (ACR >300 mg/g) will also be excluded from the analysis.

#### **4.1.1. Definition**

The primary efficacy endpoint is the time to the first occurrence of progression of albuminuria.

Urinary albumin creatinine ratio (ACR) is used to assess albuminuria. Subjects will be classified as having normoalbuminuria (ACR <30 mg/g), microalbuminuria (ACR ≥30 mg/g and ≤300 mg/g), or macroalbuminuria (ACR of >300 mg/g)].

Progression is the development of microalbuminuria or macroalbuminuria in a subject with baseline normoalbuminuria or the development of macroalbuminuria in a subject with baseline microalbuminuria, accompanied by an ACR value increase of greater than or equal to 30% from baseline.

If the ACR at a visit meets the definition of progression as described, a confirmatory ACR collection approximately 1 to 2 months later (or sooner under unusual circumstances, eg, subject is stopping study drug) should be done. In cases where a confirmatory sample is not collected within 1 to 2 months, the next available set of ACR measurements can be used for confirmation.

The primary efficacy analysis will be based on results of ACR measurements from a single visit whether confirmed or unconfirmed. The date of the progression/regression event will be defined as the visit date of the first urine sample for the potential progression/regression findings. A sensitivity analysis (see Section 4.1.4.2) will be based on results of ACR measurements from a single visit that were confirmed at a subsequent visit.

#### **4.1.2. Analysis Methods**

At each visit, the geometric mean of the duplicate measurements will be computed and used for all subsequent analyses unless otherwise specified. For ACR values below the lower quantifiable limit, the lower quantifiable limit itself will be used in the geometric mean calculation.

As the primary analysis for the primary efficacy endpoint, the time from Day 1 to first visit date observing progression (ie, using the visit date of the original sample collection and not using the visit date of the confirmatory sample collection) of albuminuria will be analyzed using a Cox proportional hazards regression model. The response variable in the model is time to progression and the model will include treatment and baseline albuminuria status as the explanatory variables. The hazard ratio of canagliflozin compared to placebo and its 95% CI will be estimated. Canagliflozin will be considered superior to placebo in the reduction of progression if the p-value of the test of significance, ie, the Wald test from the Cox model specified above, is  $\leq 0.05$  in the context of multiplicity adjustment described in Section 4.3.

For ITT analysis, endpoint events that occur during the data period (see Table 1) will be considered as eligible events; otherwise subjects will be censored at the last ACR measurement up to GTED.

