**Figure 2: Follow-up of Randomized Subjects with Respect to the GTED**

Note: Following the announcement of the GTED, investigators are not expected to continue collecting data for purposes of the clinical trial after the 30-day post-treatment contact.

In this study, duplicate urinary samples will be collected from 2 consecutive days (first morning void urine samples from the visit day and the day prior to the visit). The scheduled albumin creatinine ratio (ACR) measurements will be made on Day 1 (baseline), Week 26, Week 52, Week 78, Week 104, Week 156 and the last on-drug visit.

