###### **4.4.2.1.3. Urinary ACR**

Post-baseline ACR will be analyzed using mixed effect model repeat measurement (MMRM) and the ITT analysis set.

Since the distribution of ACR is highly skewed, the log transformed ACR values of all the post-baseline and scheduled visits will be modeled, using a linear mixed effects model. The linear mixed effects model will be fit to the logarithm of ACR as a dependent variable, including treatment, logarithm of baseline ACR value, visit, treatment by visit interaction, and logarithm of baseline ACR value by visit interaction as fixed effects. The percentage of treatment difference,

ie, treatment difference in mean ACR relative to placebo, can be calculated by taking the anti-logarithm of the estimated coefficient for the treatment group and subtracting 1. The ratio of mean ACR in treatment compared to placebo and its 95% CI will be presented. An unstructured covariance will be used to model the within subject errors.

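### Setting ACR values below the quantifiable limit to the limit shrinks the treatment ratio in the exploratory log-ACR model toward 1, by an amount the documents do not let one determine

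*SAP*

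**What the plan says.** Two first-morning specimens are taken per visit (SAP 1.1: "In this study, duplicate urinary samples will be collected from 2 consecutive days"). SAP 4.1.2 combines them: "At each visit, the geometric mean of the duplicate measurements will be computed and used for all subsequent analyses unless otherwise specified". It then adds: "For ACR values below the lower quantifiable limit, the lower quantifiable limit itself will be used in the geometric mean calculation". The substitution is thus made on each specimen, before averaging.

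SAP 4.4.2.1.3 uses these visit values in a mixed model, in which "the log transformed ACR values of all the post-baseline and scheduled visits will be modeled, using a linear mixed effects model". The terms are "treatment, logarithm of baseline ACR value, visit, treatment by visit interaction, and logarithm of baseline ACR value by visit interaction as fixed effects". The result is an effect size: "The ratio of mean ACR in treatment compared to placebo and its 95% CI will be presented". The section has no rule of its own for values below the limit, so the one in 4.1.2 carries over.

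Protocol 11.3.1 and 11.3.3 contain the geometric mean and the log-ACR model but no rule for such values. Neither document gives the limit, the expected share below it, or a sensitivity analysis for it. Urinary ACR is exploratory in both documents, and SAP section 4 says: "All statistical tests, except those for the primary and secondary efficacy endpoints, will be considered nominal".

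**The concern.** The rule is written in the primary-endpoint section, where it does little harm, because what matters there is whether ACR crosses 30 or 300 mg/g. In a continuous log-scale model it acts differently. Every value below the limit is moved up to the limit. If treatment lowers a value from just above the limit to well below it, only the first part of the fall is recorded; if the value was already below, none of it is.

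What is at stake is the reported ratio of mean ACR and its confidence interval, which would be centred too close to 1. Low values are to be expected: albuminuria is only one of several optional risk factors in one of the two entry routes (Protocol 4.2), and normoalbuminuric subjects are a planned stratum (SAP 4.1.3). How many values lie below an assay limit, however, cannot be read from the documents.

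**Working it through.** **Inputs.** From the documents: substitution at the limit per specimen, duplicates averaged on the log scale, and a model with no treatment-by-baseline-ACR term, which therefore assumes one proportional effect at each visit. Not in the documents, and so assumed over a range: the true ratio, the SD of log ACR, and the share of placebo values below the limit. The plan states no figure on this point, so there is none to reproduce.

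**Formula.** Let X = log ACR be normal with mean μ and SD s, and let c be the log of the limit. With a = (c − μ)/s,

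E[max(X, c)] = c·Φ(a) + μ·(1 − Φ(a)) + s·φ(a).

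The derivative with respect to μ is 1 − Φ(a), the share above the limit. A small shift in μ is therefore recorded at only that fraction of its size.

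**Worked case.** True ratio 0.80, s = 1.4, placebo μ = 0, 20% of placebo values below the limit, so c = 1.4 × (−0.8416) = −1.178.

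- Placebo: −1.178 × 0.200 + 0 + 1.4 × 0.2800 = 0.156.
- Canagliflozin: μ = ln 0.80 = −0.2231, a = −0.682, Φ(a) = 0.2475, φ(a) = 0.3161. This gives −1.178 × 0.2475 − 0.2231 × 0.7525 + 1.4 × 0.3161 = −0.017.
- Difference: −0.173, so the ratio is exp(−0.173) = 0.841 in place of 0.80.
- Loss on the log scale: 1 − 0.1733/0.2231 = 22.3%. Mean share below the limit: (20% + 24.75%)/2 = 22.4%.

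**Range.** True ratio 0.82, s from 1.2 to 1.6:

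| Placebo share below limit | Expected ratio | Loss of log effect |
|---|---|---|
| 1% | 0.822 | about 1% |
| 2% | 0.824 | about 2% |
| 5% | 0.83 | 6% |
| 10% | 0.84 | 11-12% |
| 20% | 0.86 | 22% |
| 30% | 0.87-0.88 | 32-33% |

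For true ratios of 0.7 to 0.9, s of 1.0 to 1.8 and placebo shares of 2% to 40%, the loss stays within about 0.3 percentage points of the share averaged over the two arms.

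**Simulation.** With 1,000,000 subjects, duplicates, substitution before averaging, and adjustment for a baseline substituted in the same way (true ratio 0.80, s = 1.4), the losses are 6.0%, 11.5%, 22.6% and 33.1% at placebo shares of 5%, 10%, 20% and 30%. A limit set on urine albumin in place of ACR gives nearly the same.

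**If the effect is not common.** At a 20% placebo share, the loss is 11% if the effect grows with ACR, 5% if it is confined to the upper half of baseline ACR, and 45% if confined to the lower half. The direction is the same in each case.

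**Primary endpoint.** Progression needs ACR of at least 30 mg/g. The 30% rise is then met automatically from any baseline below 30/1.3 = 23.1 mg/g, so a limit under about 23 mg/g hardly touches the event definition. The exception is a visit with one specimen below the limit L and the other very high: the substituted geometric mean reaches 30 only if the other is at least 900/L (180 mg/g for an illustrative L of 5 mg/g).

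**The case against.** The strongest objection is materiality. The limit, the share below it, the ACR ratio and the SD are all undocumented. Normoalbuminuria means below 30 mg/g, which is not the same as near an assay limit. Nothing in the documents makes 5-20% more plausible than 1-2%, where the loss is negligible. This stands: the mechanism is certain, its size in this trial is not.

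Second, the analysis is exploratory and its inference nominal. The rule pulls toward no effect, so it cannot create a benefit where there is none. The test statistic loses less than the estimate, about 7% at a 20% share under a common effect, because the SD falls too. This also stands and limits the importance of the point. It does not remove it, since the plan promises an effect size with an interval.

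Third, the simple size rule needs a common proportional effect. That is what the SAP model assumes, but the data need not comply, hence the condition.

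A reader might also infer that the loss falls only on canagliflozin because more of its values drop below the limit. The documents do not support this: values are raised in both arms and at baseline, and the loss follows the average share of the two arms.

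**Conclusion.** The point holds as a minor one. The rule in SAP 4.1.2 reaches the log-ACR model and attenuates its treatment ratio. Under log-normality and a common proportional effect, the loss on the log scale is about the two-arm average share below the limit. With other effect patterns the direction is the same and the size can be smaller or larger.

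Two stronger readings are tempting. One is that the reported ACR ratio is materially biased; without the limit or the share, the documents cannot show that. The other is that the main result is compromised; it is not, since progression depends on crossing 30 or 300 mg/g and the substitution hardly changes who crosses, for any limit below about 23 mg/g.

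**What to change.** Keep the substitution in SAP 4.1.2 for classifying albuminuria. In SAP 4.4.2.1.3:

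- Pre-specify an analysis of log ACR that treats post-baseline values below the limit as left-censored, at least as a sensitivity analysis beside the MMRM. Modelling the individual specimens avoids having to define censoring for a pair with one value below the limit. The substituted baseline can remain as covariate, since it is measured before treatment and handled alike in both arms.
- Report the limit and the percentage of values below it by treatment and visit. If the share is 1-2%, the table settles the matter.

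Do not simply switch to half the limit. It is equally arbitrary and can overstate the effect: at 5-10% below the limit, by about 2% of the log effect with SD 1.0 and 4-5% with SD 0.8. If log ACR is itself right-skewed (assumed gamma-shaped, SD 1.4), the overstatement is about 6-18% at a 5% share and 5-15% at 10%.

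The cost is a short SAP addition, one table and one extra model. That model relies on a log-normal assumption and, with repeated measures, takes more than one line of programming.

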11.3. Efficacy Analyses

11.3.1. Primary Efficacy Analysis

In this study, duplicate urine specimens will be collected for all ACR measurements. At each visit, the geometric mean of the duplicate measurements will be computed and used for all subsequent analysis unless otherwise specified.

Subjects will be classified as having normoalbuminuria (urinary ACR of <3.5 mg/mmol [<30 mg/g]), microalbuminuria (ACR ≥ 3.5 mg/mmol [≥ 30 mg/g] and ≤ 35 mg/mmol [≤ 300 mg/g]), or macroalbuminuria (ACR of >35 mg/mmol [>300 mg/g]).

The primary efficacy analysis seeks to demonstrate the superiority of canagliflozin in the reduction of albuminuria progression relative to placebo.

The time from first study drug administration to first visit date observing progression (ie, not using the visit date of the repeat sample collection) of albuminuria will be analyzed using a Cox proportional hazards regression model. The model will include treatment and baseline albuminuria status as covariates. The hazard ratio between canagliflozin and placebo will be provided, including its 95% confidence interval. The observation period for this time-to-event analysis will include all available measurements from first study drug administration to the visit date of the last ACR measurement. Subjects with no progression will be censored at the visit date of the last albuminuria measurement.

As a sensitivity analysis, the actual onset time of progression of albuminuria can be determined to lie within an interval from a sequence of examination times (ie, data are interval censored). As a supportive analysis, the accelerated failure time (AFT) model with log normal error structure will be implemented considering interval censoring. The dependent variable in AFT model is logarithm of time to progression of albuminuria. The model will include treatment group and baseline albuminuria status as covariates. We can use speed of progression to interpret AFT model. For any time (t), the probability of a subject on placebo progression-free beyond time t is the probability of a subject on canagliflozin progression-free beyond t/α , where α is the acceleration factor which can be estimated from the model. Additional sensitivity analyses will be specified in the study SAP.

The cumulative progression rate derived from Kaplan-Meier estimate will be displayed graphically to evaluate the timing of progression and the consistency of the treatment effect over time.

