#### **Imputation model**

Assuming that after treatment discontinuation, subjects discontinued from the canagliflozin arm will exhibit a response similar to subjects in the placebo arm, the imputation model will be fit using the non-missing data in the placebo group and adjusted for covariates that may be related to the missing data mechanism and the risk of progression based on clinical judgment. The potential covariates include:

- Baseline ACR (continuous);
- Baseline eGFR categories (30 to <60, 60 to <90,  $\geq 90$  mL/min/1.73m^2);
- Baseline blood pressure (SBP<140, DBP<90 mmHg): Yes/No;
- Baseline HbA1c  $\geq 8\%$ : Yes/No;
- Age group: <65,  $\geq 65$  years old;
- Race: White, Other;
- Sex: Male, Female;

In case of convergence issues, the covariates will be removed from the model in the descending order of the list (ie, starting from the bottom of the list).

Due to the highly skewed data of ACR, both baseline and post baseline ACR in the imputation model will be log transformed.

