### **Analysis summary**

The imputed data will be re-analyzed using the same Cox model for the primary analysis (see Section 4.1.2). The imputation process will be repeated 1000 times and the multiple versions of analysis results will be combined into single inferential summary using Rubin’s rule.

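### The primary Cox model adjusts for a two-level albuminuria category but not for the baseline ACR value already collected, so it probably gives up some power

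*SAP*

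**What the plan says.** - Primary model: SAP 4.1.2 states that "the model will include treatment and baseline albuminuria status as the explanatory variables", with the Wald test from that model as the test of significance. Protocol 11.3.1 agrees: "The model will include treatment and baseline albuminuria status as covariates".
- Levels of the covariate: under SAP 4.1, "subjects with macroalbuminuria at baseline (ACR >300 mg/g) will also be excluded from the analysis". Normo- and microalbuminuria remain, as the subgroup list in SAP 4.1.3 confirms.
- Endpoint: SAP 4.1.1 defines progression as moving up an albuminuria category (cut-points 30 and 300 mg/g), "accompanied by an ACR value increase of greater than or equal to 30% from baseline".
- Availability of the value: SAP 1.1 says the scheduled ACR "measurements will be made on Day 1 (baseline), Week 26, Week 52, Week 78" and at later visits, in duplicate. SAP 4.1 already drops subjects without a baseline ACR from the primary analysis.
- Use elsewhere: the imputation model in SAP 4.1.4.3 is "adjusted for covariates that may be related to the missing data mechanism and the risk of progression based on clinical judgment", and continuous baseline ACR heads its list. Covariates are dropped from the bottom if the model does not converge, so baseline ACR would go last. Log baseline ACR is also a fixed effect in the mixed model for ACR (SAP 4.4.2.1.3).
- After imputation: "The imputed data will be re-analyzed using the same Cox model for the primary analysis", that is, the model with category only.

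**The concern.** The endpoint is built from the variable that the model reduces to two levels. A subject just below a threshold and one far below it in the same category are given the same baseline hazard, although the rise each needs is very different. In a Cox model, omitting a strong prognostic covariate pulls the estimated log hazard ratio toward zero and so lowers power, even when treatment is randomized. Randomization here was unstratified (SAP 1.2), so chance imbalance in baseline ACR within a category is not controlled by design either.

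Progression of albuminuria is the only primary endpoint. The stake is power for that test, not its validity.

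**Working it through.** **1. The plan's own figure.** Inputs from protocol 11.2: 693 events, 22% reduction (HR 0.78), two-sided 0.05; 1:1 allocation from protocol 6.1.

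|ln 0.78| × √693 / 2 = 0.2485 × 26.32 / 2 = 3.27; power = Φ(3.27 − 1.96) = Φ(1.31) = 90.5%.

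The figure reproduces with no covariate gain. Hazards of 0.074 and 0.074 × 0.78, 10% annual discontinuation, 18 months' uniform accrual and 36 months in total give about 696 events, against 693 stated.

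**2. Rise needed within a category.** The effective threshold is max(30 or 300, 1.3 × baseline). For normoalbuminuric subjects:

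| Baseline (mg/g) | Must reach (mg/g) | Fold rise |
|---|---|---|
| 5 | 30 | 6.0 |
| 20 | 30 | 1.5 |
| 28 | 36.4 (30% rule binds) | 1.3 |

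**3. Threshold-crossing simulation.** From the documents: the SAP 4.1.1 endpoint with the 30% rule, ACR at weeks 26, 52, 78, 104 and 156 plus the last on-drug visit, and 10% discontinuation per year. Follow-up was uniform over 1.5 to 3 years. Assumed: the ACR distributions, about 70% normoalbuminuric and a quantification floor of 3 mg/g. Each trial had about 5,300 to 5,400 subjects without macroalbuminuria, calibrated to about 693 events and a category-only HR of 0.78 to 0.79. There were 2,000 alternative and 2,000 null trials per scenario (Monte Carlo SE about 0.5 to 0.7 points for power).

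Information ratio = ((1.96 + z of adjusted power) / (1.96 + z of category-only power))². For A: ((1.96 + 1.75) / (1.96 + 1.25))² = 1.34. Last column: Φ(3.27 × √ratio − 1.96).

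| Scenario (between-, within-subject log SD) | Category only | + log ACR, robust variance | Ratio | Applied to 90.5% |
|---|---|---|---|---|
| A (1.25, 0.30) | 89.4% | 96.0% | 1.34 | 97% |
| B (1.25, 0.45) | 87.6% | 93.2% | 1.23 | 95% |
| C (1.40, 0.55) | 89.2% | 94.4% | 1.23 | 95% |
| D (as A; 15% rise 1.0 log unit/year whatever their baseline) | 88.6% | 93.0% | 1.18 | 94% |
| E (extreme: 15% rise 2.0 log units/year) | 87.7% | 88.6% | 1.03 | 91% |

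The HR moves from 0.78–0.79 to 0.74–0.78.

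Null rejection: 4.0–5.1% category only; 4.3–5.4% with log ACR and robust variance; 4.7–6.1% with log ACR and model-based variance. The robust variance costs at most 0.9 points of power.

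Functional form: separate slopes by category change power by at most 0.3 points. Using log distance to the effective threshold instead adds 0 to 1 point.

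**4. Second set of simulations, different assumptions.** Ratio = (mean Wald z adjusted / mean Wald z category only)².

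- Proportional hazards, 600 trials each: for an HR per within-category SD of log ACR of 1.0, 1.5, 2 and 3, the ratio is 1.00, 1.02, 1.07 and 1.24. Applied to the planned 90.5%, power is 90.5%, 91.1%, 92.3% and 95.3%. The standard error ratio is 1.000–1.001, so the gain comes from a less attenuated log HR.
- Threshold crossing (median 12 mg/g, log SD 1.3, visit noise 0.25 to 0.6; 250 trials each): the ratio is 1.15 to 1.38, or power of about 94% to 97%. The category-only HR was about 0.78 in three scenarios and 0.76 in the fourth.

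**The case against.** **It is a preference, not a defect.** The model is valid, protocol and SAP agree, and planned power is already 90.5%. All of that stands, and it is why this is a recommendation rather than a correction.

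**The other models are not comparable.** In the imputation and mixed models ACR is the continuous response, so its baseline value is the natural covariate. For event endpoints the SAP uses categorical baseline terms throughout. This weakens the argument from inconsistency. It does not touch the main argument, which is that the event is itself an ACR threshold crossing.

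**The size rests on assumption.** Correct. No document gives the ACR distribution, visit-to-visit noise or prognostic strength, and zero gain is possible. It would require baseline ACR to be uninformative within category, which is hard to square with the endpoint definition.

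**The estimand changes.** Power rises because the conditional log HR is larger, not because the standard error falls, and the HR is then not directly comparable with the planning value of 0.78. This stands as a cost. The planned HR is, however, already conditional on category.

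**A linear log-ACR term is approximate.** The 30% rule and the quantification limit both bend the relation, and model-based null rejection reached 6.1% in one scenario. The robust variance is needed for this reason.

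**The confirmatory test is conditional.** Under SAP 4.3 it proceeds only if the integrated MACE and mortality tests succeed, so the confirmatory gain counts only then. If that happened with probability 50% to 80% (assumed, independent), 1 to 7 points would become about 0.5 to 5.6.

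**It is late.** Recruitment is complete, and SAP 4.1.4.3 already describes features of the collected ACR data. The change must therefore be justified by the endpoint definition and dated before unblinding.

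**Conclusion.** The concern holds as a missed efficiency gain in a valid analysis. Adding log baseline ACR would probably raise power for the primary test by about 1 to 7 points, taking 90.5% to about 91% to 97%. The information ratio is 1.03 to 1.34 in the main scenarios, and 1.00 to 1.38 once the second set is included. The direction follows from the endpoint definition. The size depends on assumed ACR distributions, noise and prognostic strength, so confidence in it is moderate. Much of the HR shift reflects the conditional estimand and should not be read as removal of bias.

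**What to change.** Before unblinding, specify in SAP 4.1.2, protocol 11.3.1 and the protocol synopsis a Cox model with treatment, baseline albuminuria status and log baseline ACR (geometric mean of the duplicates). Take the Wald test and 95% CI from the robust (sandwich) variance. Keep the category-only model as a named sensitivity analysis.

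The on-treatment analysis (SAP 4.1.4.1) and the missing-data analysis (SAP 4.1.4.3) inherit the model by reference. Subgroup models (4.1.3) and the supportive Cox models (4.1.4.2) are also built on the primary model, so state which form they use. No change is proposed for the AFT model or for regression of albuminuria. Because SAP 4.4.2.1.2 models regression in a similar way to progression, one sentence should say that its covariates are unchanged.

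Cost: a dated amendment to both documents, an HR conditional on baseline ACR, and a robust standard error that cost at most 0.9 points of power in simulation. No new data are needed. No further subjects are lost, since those without a baseline ACR are already excluded.
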